### 3.1.1. Safety Assessments

At Visit 1 (Day 1) and each monthly and quarterly visit, the following assessments will be completed:

- Review vital signs, clinical labs, ECG, urinalysis, and physical examination (including height and weight). Refer to Section 6.1.
- Review adverse events (AEs). Refer to Section 6.1.8.
- 12-lead ECG.
- Brief neurological exam. Refer to Section 6.1.2.

At Visit 7 (End of Study) or Early Withdrawal Visits the following assessments will be completed:

- Columbia-Suicide Severity Rating Scale (C-SSRS) will be used for children and adolescents aged 7 to 17 years, if appropriate. Refer to Section 6.1.6.
- Review vital signs, clinical labs, ECG, urinalysis, and physical examination (including height and weight). Refer to Section 6.1.
- Review AEs. Refer to Section 6.1.8.
- Brief neurological exam. Refer to Section 6.1.2.

All AEs that arise during the Safety, Taper, and Follow-up Periods will be documented. Overall, patient safety will be reviewed as described in Section 10.3.

### 3.1.2. Taper Period

At the end of the Long-Term Safety study patients will be tapered off of CBD over a 0-10 days period. The following tapering scheme will be utilized: 40 mg/kg/day will be reduced to 30 mg/kg/day for five days, then 20mg/kg/day for five days; 30mg/kg/day will be reduced to 20mg/kg/day for five days; and doses  $\leq$  20 mg/kg/day can be discontinued without taper. This can be modified by the investigator based upon the patient's response

[figure not shown]
Tapering will occur under the following circumstances:

- Patient completes Visit 7 (End of Study) of INS011-17-113.
  - Patient will begin tapering the day after Visit 7.
- Patient withdraws early.
  - Patient will begin tapering the day after the investigatory has been informed of the decision to withdraw from the trial.

**3.1.3. Follow-Up Period**

A follow-up telephone call (Visit 9) will occur 30 days after the Visit 7 (End of Study) or Early Withdrawal to assess AEs, AEDs, and record concomitant medications.

Approved

**Figure 1: Study Design Schematic**

### 3.2. Patient Selection

#### 3.2.1. Inclusion Criteria

Patients must meet all of the following inclusion criteria:

1. Completed all activities through Visit 6 (End of Study) of INS011-17-103.
2. Patient and/or parent(s)/caregiver(s) fully comprehend the informed consent form (ICF) and assent form, understand all study procedures, and can communicate satisfactorily with the investigator and study coordinator, in accordance with applicable laws, regulations, and local requirements.
3. A female patient is eligible to participate in the study if she is:
  - a. Premenarchal, or
  - b. Of childbearing potential with a negative urine pregnancy test at the Screening Visit. If sexually active, she must agree to fulfill one of the following requirements:
    - i. Complete abstinence from intercourse for  $\geq$  4 weeks prior to administration of the first dose of the investigational product, throughout the Safety Period, and 4 weeks after completion or premature discontinuation from the investigational product, and agreement to use a double barrier method if she becomes sexually active.
    - ii. Use of acceptable methods of contraception throughout the study and 4 weeks after completion or premature discontinuation from investigational product. The acceptable method of contraception is double barrier method (i.e., condom plus spermicide or a condom plus intrauterine device [IUD], diaphragm, or stable hormonal contraceptive use for at least 3 months before screening and through 14 days after study completion).
4. A sexually active male patient or partner of enrolled patient must be willing to use acceptable methods of contraception throughout the study and for 4 weeks after completion of study participation or discontinuation from investigational product. The acceptable methods of birth control are abstinence or double barrier birth control (i.e., condom plus spermicide or a condom plus one of the methods listed in criterion #3).
5. In the opinion of the investigator, the parent(s)/caregiver(s) is (are) willing and able to comply with the study procedures and visit schedules, including venipuncture, and the visit schedules.

#### 3.2.2. Exclusion Criteria

Patients will be excluded for any of the following:

1. Patient or parent(s)/caregiver(s) have daily commitments during the study duration that would interfere with attending all study visits.
2. Experienced an anoxic episode related to study drug requiring resuscitation during their previous study.

3. Developed an adverse event thought to be related to CBD in the previous study and for whom the Investigator determines that continuing treatment with CBD would not be in the best interest of the patient.
4. Evidence of other clinically significant disease such as unstable hepatic, hematological, renal, cardiovascular, gastrointestinal, immunological, or pulmonary diseases or ongoing malignancies.
5. Compromised respiratory function or severe respiratory insufficiency.
6. Clinically significant abnormal laboratory values within the past 14 days, including:
  - a. Liver function tests (LFTs) such as albumin, direct bilirubin, total bilirubin, aspartate aminotransferase (AST), and alanine aminotransferase (ALT)  $\geq$  3 times the upper limit of normal (ULN).
7. In the opinion of the investigator, the patient is unsuitable in any other way to participate in this study.

### **3.3. Removal of Patients from Therapy or Assessment**

Patients will be allowed to discontinue their participation in the study at any time for any reason (withdrawal of consent). Furthermore, participation in this clinical study may be discontinued by the investigator or by the sponsor for any of the following reasons:

- Intolerable side effects of the study product.
- Changes in medical status or medical condition of the patient such that the investigator believes that patient safety will be compromised or that it would be in the best interest of the patient to stop treatment.
- Patient safety or welfare is at risk.
- Non-compliance with study visits, defined as failure to perform any portion of scheduled assessments or procedures.
- Any unforeseen event that in the opinion of the treating physician and/or the Principal investigator, will prevent the research participant from continuing in this study.
- Sponsor decides to stop the study.

In the event of a patient's withdrawal, the investigator will promptly notify the sponsor. Every effort will be made to complete the end-of-study assessments.

Should any patient choose to withdraw early from the study, they will be advised of the safety precautions to be taken and will be followed until resolution of any AE or until the unresolved AEs are judged by the investigator to have stabilized.

### **3.4. Dose Adjustment Criteria**

Doses of CBD may be adjusted at the investigator's discretion up to a maximum of 40 mg/kg/day only if the Data Monitoring Committee has approved the higher dose level in INS011-17-103. Doses greater than 40 mg/kg/day are not allowed. All dose changes must be clearly documented in the eCRF.

Antiepileptic drugs (AEDs) or therapies (e.g., VNS and ketogenic diet) may be initiated, discontinued or dose adjusted as needed. Any changes must be documented in the eCRF.

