**Table 1: Schedule of Events**

ASSESSMENTS	SAFETY PERIOD				Early Withdrawal	TAPER PERIOD	FOLLOW-UP PERIOD i	
	Visit Number	1 a	2, 3, 4 (monthly)	5, 6 (quarterly)				
Study Time Points	Day 1	Weeks 4, 8, 12		Weeks 24, 36	End of Active Treatment (Week 48)		0-10 Days	30 Days After EOS
Visit Window (Days)	± 5	± 5		± 5	± 3			± 5
Informed consent **								
Review of inclusion/exclusion criteria **								
C-SSRS					X	X		
Review of AEDs	X	X	X		X	X		X
Review Concomitant Medications	X	X	X		X	X		X
Vital Signs b	X	X	X		X	X		
Clinical Labs c	X	X	X		X	X		
12-lead ECG	X	X	X		X	X		
Urinalysis	X	X	X		X	X		
Urine pregnancy screen for post-menarchal females	X				X	X		
Physical Examination d	X	X	X		X	X		
Brief neurological Examination e	X	X	X		X	X		
Dosing with Cannabidiol Oral Solution f	X	X	X		X f	X g		
Drug Accountability	X	X	X		X	X		X
AEs	X	X	X		X	X		X

ASSESSMENTS	SAFETY PERIOD					TAPER PERIOD	FOLLOW-UP PERIOD i
Visit Number	1 a	2, 3, 4 (monthly)	5, 6 (quarterly)	7 (End of Study)	Early Withdrawal	8	9 (Phone Call)
Study Time Points	Day 1	Weeks 4, 8, 12	Weeks 24, 36	End of Active Treatment (Week 48)		0-10 Days	30 Days After EOS
Visit Window (Days)	± 5	± 5	± 5	± 3			± 5
End of Study				X	X h		

\*\* To be completed prior to enrollment into LTS, specifically within the 2 week period that is allotted post completion of Visit 6 (End of Study) of INS011-17-103.

a For patients who enroll within the first 2 weeks after completion of Visit 6 (End of Study) of INS011-17-103 protocol.

b Vital signs will be taken after a 5-minute seated rest.

c If the total bilirubin laboratory value is abnormal, direct bilirubin will be drawn.

d The physical examination will include height, weight, and evaluation of general appearance, skin, eyes, ears, nose, throat, neck, lymph nodes, chest, heart, abdomen, and extremities.

e A brief neurological examination (mental status, cranial nerves, nystagmus, motor system, sensory system, reflexes, coordination, gait, and station) will be performed at all visits

f At-home doses will be recorded in the daily medication diary.

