### 3. INVESTIGATIONAL PLAN

#### 3.1. Overall Study Design

This is a multicenter, open-label, flexible dose study designed to assess the long-term safety and tolerability of CBD in doses ranging from 20 mg/kg/day to 40 mg/kg/day in patients with treatment-resistant childhood absence seizures. Patients must have completed INS011-17-103 to be eligible.

The Investigator will ensure that the patients legal representative [parent(s)/caregiver(s)] will receive a copy of the informed consent form for review and provide full informed consent prior to study participation.

Patients should enroll in Long-Term Safety Study (INS011-17-113) after completing Study INS011-17-103 Visit 6 (End of Study) to avoid interruption of the investigational product. Patients will have up to 2 weeks to enroll in INS011-17-113. The first visit (Visit 1) for INS011-17-113 will be after the completion of Visit 6 of INS011-17-103.

Patients will continue to receive CBD treatment for approximately 48 weeks. Patients will remain on their assigned dose or may be titrated up to a higher dose level if the Data Monitoring Committee has approved the higher dose level in INS011-17-103. **If any participant does not enroll within the 2 week window, the patient will not be eligible to enroll into the study.**

The study will consist of a Safety Period (48±2 weeks), Taper Period (10±3 days), and a Follow-up Period (30±5 days). Treatment visits will be scheduled monthly for the first 3 months and then quarterly over the remaining 9 months. All patients will complete a Visit 7 (End of Study) or Early Withdrawal Visit regardless of when they stop treatment/complete the study. A Follow-Up telephone call (Visit 9) will occur 30 days after the end of either the End of Study (Visit 7) or Early Withdrawal.

In this study, all patients will be dosed as follows:

- Once the informed consent for INS011-17-113 is provided within the required time frame, initially the patient will receive the same dose as was administered during INS011-17-103. If tolerability issues occurred during INS011-17-103, the dose can be decreased if the dose was greater than 20 mg/kg/day. If the patient received 20 mg/kg/day and the physician wants to decrease the dose, the patient should be discontinued.

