- Physicians will not increase a patient's assigned dose until the Data Monitoring Committee has deemed that the higher dose is safe in INS011-17-103. Doses of CBD may be adjusted at the investigator's discretion up to a maximum of 40 mg/kg/day.
- Treatment with established antiepileptic drugs (AEDs) and therapeutic treatments (e.g., vagus nerve stimulation [VNS]) may be initiated/continued/adjusted and changes will be permitted as necessary based on safety concerns or changes in seizure control. Any changes must be documented in the eCRF.

Patients will be dosed approximately every 12 hours with food to help ensure consistent plasma levels are achieved. Patients will be dosed for 48 weeks during which the investigator will assess safety and tolerability.

The study will be terminated upon one of the following:

- The investigational product is successfully approved for marketing in the US.
- Sponsor elects to terminate INS011-17-113.
- The patient has received 48 weeks of treatment.

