### 3.5. Stopping Rules

The investigator reserves the right to terminate the study in the interests of patient safety and welfare. The Sponsor reserves the right to terminate the study at any time for administrative reasons.

Patients will also be discontinued from the study if they meet the following criteria:

- ALT or AST  $> 3 \times$  ULN with (or the appearance of) fatigue, nausea, vomiting, right upper quadrant pain or tenderness, fever, rash, and/or eosinophilia  $> 5\%$
- ALT or AST  $> 8 \times$  ULN
- ALT or AST  $> 5 \times$  ULN for more than 2 weeks
- ALT or AST  $> 3 \times$  ULN and bilirubin  $> 2 \times$  ULN or INR  $> 1.5$

For patients meeting the above criteria, the investigator will arrange for the patient to return to the investigational site as soon as possible (within 24 hours of notice of abnormal results) for repeat assessment of ALT, AST, bilirubin, and alkaline phosphatase (ALP), detailed history, and physical examination. Patients will be followed until all abnormalities have normalized (in the investigator's opinion) or returned to the baseline state. If the patient is unable to return to the investigational site, repeat assessments may be performed at a local laboratory.

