Previous clinical trial experience has shown that somnolence, diarrhea, and transaminase elevations may be associated with CBD treatment. Therefore, Insy Development Company has identified these as Adverse Events of Special Interest.

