#### 7.1.2. Monthly (Visits 2, 3, and 4) and Quarterly (Visits 5 and 6) Visits

The following procedures and assessments will be performed:

- Review/Assess past/current AEDs and concomitant medications.
- Record vital signs, collect blood samples for clinical labs, complete 12-lead ECG, and collect urine sample for urinalysis.
- Perform physical and brief neurological examinations.
- Collect/review/dispense CBD (dose may be modified up to 40 mg/kg/day at investigator's discretion).
- Perform drug accountability.
- Review AEs.

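### Doses may rise at any time in the 48 weeks, but laboratory tables by visit and adverse-event tables by modal dose show neither current dose nor time since an increase, and the next scheduled liver test can be 84 days away

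*Combined protocol and SAP*

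**What the plan says.** **Dosing.** Section 3.1 states the condition for any increase: "Physicians will not increase a patient's assigned dose until the Data Monitoring Committee has deemed that the higher dose is safe in INS011-17-103". Section 3.4 repeats it, allowing changes "up to a maximum of 40 mg/kg/day only if the Data Monitoring Committee has approved the higher dose level in INS011-17-103", and requires every dose change to be recorded in the eCRF. Neither section limits when in the 48 weeks an increase may happen. Section 7.1.2 places dose changes at the monthly and quarterly visits: "dose may be modified up to 40 mg/kg/day at investigator's discretion". Section 7.1.1 says the same for Visit 1.

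**Schedule.** Section 3.1: "Treatment visits will be scheduled monthly for the first 3 months and then quarterly over the remaining 9 months". Table 1 sets Day 1 and Weeks 4, 8, 12, 24, 36 and 48. Section 6.1.5 draws blood, including ALT, AST and total bilirubin, at those visits or at Early Withdrawal. No section schedules an assessment after a dose increase.

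**Events of interest.** Section 6.1.8.1 notes that "somnolence, diarrhea, and transaminase elevations may be associated with CBD treatment" and makes these three adverse events of special interest.

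**Analysis.** Section 8.4.3.2 gives descriptive statistics for laboratory values at each visit in Table 1. The synopsis (Statistical Methods) summarises laboratory values, changes and shifts for all patients together. Section 8.4.3.1 groups treatment-emergent adverse events by modal dose, meaning the dose a child took for most time on study. The synopsis also mentions summaries by dose cohort where appropriate, without defining the term for this study.

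**The concern.** Under flexible dosing, a result is informative about a dose only if the reader knows which dose the child was on and for how long. The planned summary tables show neither. A Week 36 ALT from a child eight months on one dose and one from a child raised a few weeks earlier enter the same row. An event that begins at a higher dose can be tabulated under a lower one.

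This matters most for the events the sponsor has singled out. Section 1.3 reports diarrhea and somnolence as dose-dependent in INS011-14-029, and both are events of special interest here. Transaminase elevation is the third such event and also drives the discontinuation criteria in Section 3.5. If higher-dose events are counted under a lower dose, the lower dose looks worse and the higher dose better than they were.

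The visit schedule adds to this. Scheduled tests are most frequent just after Visit 1, when children by default continue the dose from INS011-17-103, and least frequent from Week 12 on, when increases are still allowed.

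**Working it through.** The documents state no interval from dose change to test, so there is no planned figure to reproduce. The check is calendar arithmetic on Table 1.

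**1. Time to the next scheduled liver test.** Inputs: visit weeks 0, 4, 8, 12, 24, 36, 48; windows ±5 days, but ±3 at Visit 7. Gap = (next visit week − week of increase) × 7. Range = gap ± (sum of the two windows). The last column assumes no further change and no early withdrawal.

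| Increase made at | Next test | Gap (days) | With windows | Scheduled results left at new dose |
|---|---|---|---|---|
| Visit 1, 2 or 3 | 4 weeks on | 4 × 7 = 28 | 28 ± 10 = 18 to 38 | 6, 5 or 4 |
| Visit 4 (Week 12) | Week 24 | 12 × 7 = 84 | 84 ± 10 = 74 to 94 | 3 |
| Visit 5 (Week 24) | Week 36 | 12 × 7 = 84 | 84 ± 10 = 74 to 94 | 2 |
| Visit 6 (Week 36) | Week 48 | 12 × 7 = 84 | 84 ± 8 = 76 to 92 | 1 |

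The later gap is 84/28 = 3 times the earlier one. The 84-day spacing covers (48 − 12)/48 = 75% of the treatment period. For an increase d days after a visit in that phase, the nominal gap is 84 − d; with d = 28 it is 56 days.

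**2. Modal-dose label.** Take a completer with one increase at week T, taper days left out. Time at the lower dose is T weeks; time at the higher dose is 48 − T. The lower dose is modal when T > 48 − T, that is, T > 24.

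- T = 36: 36 against 12 weeks. The label is the lower dose, so events starting in the 12 weeks at the higher dose (12/48 = 25% of treatment) are counted under the lower one.
- T = 12: 12 against 36 weeks. The label is the higher dose, so events from the first 12 weeks (25%) are counted under a dose not yet taken.
- T = 24: 24 against 24 weeks, a nominal tie. The definition gives no rule for ties.

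The Week 24 cut-off holds for a single increase only. With increases at Weeks 12 and 24 the times are 12, 12 and 24 weeks, and events from the first two doses are counted under the third.

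**3. Laboratory tables.** In the Week 24, 36 and 48 rows, children raised at the previous visit have about 12 weeks at their dose, while children never raised have 24, 36 or 48 weeks in this study plus their time in INS011-17-103. A by-visit pooled row cannot separate them.

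**The case against.** **Against the analysis point.** The objective is long-term safety under flexible dosing, and pooled tables do not claim to describe any one dose. All safety data are listed by visit, out-of-range values are listed, and dose changes are recorded, so a reader could trace each case. Section 8.4 calls itself a summary and leaves detail to an SAP finalised before database lock. With at most 30 patients, tables by time since increase will have small cells. The last point stands and is the real cost. The others do not repair the summary tables: modal dose is a deliberate by-dose presentation, and it files some events under a dose the child was not taking at onset. The undefined dose cohort, if it means starting or modal dose, still gives each child one fixed label.

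**Stronger readings the documents do not support.**

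- A reader might infer that every increase after Week 12 leaves 84 days without a test. That is exact only for an increase at Visit 4, 5 or 6. Between visits the gap is shorter, and Section 6.1.8.1 allows extra tests at discretion to follow an event.
- A reader might infer that the earliest children on the lowest dose will mostly be raised in the quarterly phase. That depends on cohort order and on committee timing in INS011-17-103, which are not given. If levels were cleared early, increases could fall at Visits 1 to 3, with 28-day gaps.
- A reader might take the 91% of subjects above 20 mg/kg/day in INS011-14-030 as a forecast of frequent increases. That study followed cohorts at 10, 20 and 40 mg/kg/day; here children enter at 20, 30 or 40, so being above 20 need not involve an increase.
- A reader might infer that Sections 3.4 and 7.1.2 contradict Table 1, so that a liver sample must be added. One permits dose changes and the other sets visits; they do not conflict. A sample timed from an increase would be a new clinical rule.

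**Conclusion.** The point holds as an analysis gap, with a schedule fact behind it. The next scheduled liver test after an increase at Visit 4, 5 or 6 is 84 days away (74 to 94 days; 76 to 92 to Visit 7), and less after an increase between visits. The Week 24 to 48 laboratory tables pool children with very different times at their current dose. For a completer with one increase, modal dose moves higher-dose events to the lower dose when the increase comes after Week 24, and lower-dose events to the higher dose when it comes before.

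The arithmetic rests on nominal visit weeks, completion of 48 weeks and, for the Week 24 cut-off, a single increase. The number of children affected is unknown: it lies between none and all of the at most 30 enrolled, because the committee's timing in INS011-17-103 is not in the documents. The point does not show that the visit schedule is wrong.

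**What to change.** Keep the planned tables and add the following, in Sections 8.4.3.1 and 8.4.3.2 or in the SAP before database lock:

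- **Adverse events:** treatment-emergent events by dose at onset and by time since the last dose increase, with the number of children exposed and the weeks at each dose as denominators.
- **Liver tests:** ALT and AST by current dose at sampling and by time since the last increase.
- **Coverage:** the number of dose increases with no liver test before the next quarterly visit, so that the reader can see how much of the early period after an increase was observed.

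The dose-change records already required in the eCRF supply the inputs, so no new data are collected. The cost is some programming and sparse tables; with at most 30 patients, counts should be shown beside any percentage. The tables remain descriptive, because children who are raised are likely to be those who tolerated the lower dose.

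Separately, the sponsor should consider whether flexible dosing in Sections 3.4 and 7.1.2 and the fixed schedule in Table 1 fit together. No sampling rule or interval is proposed here.

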### **4.7.2. Prohibited Therapies**

During the Safety, Taper, and Follow-up Periods, patients are not to receive the following:

- Any cannabinoids besides the study drug (cannabidiol,  $\Delta^9$ -THC, hemp oil, Realm Oil or marijuana).
- Phenytoin, fluvoxamine, carbamazepine, or St. John's Wort.
- Medications that are strong inhibitors/inducers/sensitive substrates with a narrow therapeutic index for CYP3A4, CYP2C9, or CYP2C19, with the exception of Valproic Acid.
- Any other investigational drug or investigational device.

Although they are not prohibited, patients taking concomitant medications may need to be monitored with special care to identify any AEs arising due to the potential for altered drug metabolism.

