### 7.1. Safety Period

#### 7.1.1. Visit 1 (Day 1)

The following procedures and assessments will be performed:

- Review/Assess past/current AEDs and concomitant medications.
- Record vital signs, collect blood samples for clinical labs, and collect urine sample for urinalysis.
- Urine dipstick pregnancy test (all female patients of childbearing potential).
- Perform physical and brief neurological examinations.
- 12-lead ECG.
- Collect/review/dispense CBD (dose may be modified up to 40 mg/kg/day at investigator's discretion).
- Perform drug accountability.
- Review AEs.

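### The antiepileptic-drug permissions in the synopsis, 3.1 and 3.4 conflict with the prohibited list in 4.7.2, and no eligibility criterion names the listed therapies

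*Combined protocol and SAP*

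**What the plan says.** Permission. Section 3.4 states: "Antiepileptic drugs (AEDs) or therapies (e.g., VNS and ketogenic diet) may be initiated, discontinued or dose adjusted as needed". Section 3.1, repeated in the synopsis under Methodology, says that established antiepileptics and treatments such as vagus nerve stimulation "may be initiated/continued/adjusted and changes will be permitted as necessary based on safety concerns or changes in seizure control". All three places require changes to be recorded in the eCRF. None mentions section 4.7.2.

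Prohibition. Section 4.7.2 opens: "During the Safety, Taper, and Follow-up Periods, patients are not to receive the following". Its list covers cannabinoids other than the study drug, other investigational drugs or devices, "Phenytoin, fluvoxamine, carbamazepine, or St. John's Wort", and "Medications that are strong inhibitors/inducers/sensitive substrates with a narrow therapeutic index for CYP3A4, CYP2C9, or CYP2C19, with the exception of Valproic Acid".

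Link between the two. Section 4.7.1 permits other medication at the investigator's discretion, but only outside the 4.7.2 list. It is the only place that defers to that list.

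Entry. The criteria appear twice, in the synopsis and in 3.2.1 and 3.2.2. Neither copy refers to the therapies in 4.7.2. Exclusion 7 leaves general unsuitability to the investigator's opinion.

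Stated safeguard. Section 1.6 lists CYP interaction as an area of potential concern. It says that the eligibility criteria, the concomitant medication guidelines and safety monitoring are meant to keep such risks low.

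**The concern.** Two operative rules give different answers for the same drugs. Section 1.2.2 itself describes phenytoin and carbamazepine as anti-seizure drugs, so they fall under the antiepileptic permission as well as under the prohibition. A site working from the synopsis or 3.4 may start one of them; a site working from 4.7.2 may not.

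The entry criteria do not settle the matter, although section 1.6 counts them among the safeguards against this kind of interaction. Sites could treat identical patients differently: enrol and record a deviation, change the background treatment, or refuse entry.

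The consequence for the analysis is interpretive. Safety and tolerability are the only objective (section 2), at most 30 patients will be enrolled (8.2), and treatment-emergent adverse events are summarised descriptively by modal dose group (8.4.3.1). Baseline is Visit 6 of INS011-17-103 (8.1). A listed drug begun between that visit and Visit 1 starts after baseline and before Day 1, so any effect it has on laboratory values would count as change from baseline. No planned adverse event table or listing marks such patients.

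**Working it through.** No rate, power figure or sample-size formula is involved. The check sets the passages side by side.

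1. When the prohibition applies. Section 4.7.2 covers the Safety, Taper and Follow-up Periods. Section 7.1 lists Visit 1 (Day 1) as the first visit of the Safety Period. The prohibition therefore runs from Visit 1 to the end of the study.

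2. Which drugs fall under both rules. At least phenytoin and carbamazepine: named in 4.7.2, and described as anti-seizure drugs in 1.2.2. Any other antiepileptic that meets the CYP description in 4.7.2 would join them; the documents name only valproic acid as an exception.

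3. Whether the permission is limited.
   - Synopsis and 3.1: limited to established antiepileptics, with changes tied to safety or seizure control. No exception for 4.7.2 drugs.
   - 3.4: initiation, discontinuation or dose adjustment, with neither of those limits and no exception. It does not mention continuation; that word comes from the synopsis and 3.1.
   - 4.7.1: subject to 4.7.2.

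4. Whether entry is screened. There are 5 + 7 = 12 criteria. The number that refer to the therapies in 4.7.2 is 0, in both copies. Exclusion 7 could be used, but only at the investigator's discretion.

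5. Case at entry. Up to 2 weeks may pass between Visit 6 of INS011-17-103 and enrolment (3.1). Suppose a listed antiepileptic is started in that interval. Inclusion 1 is met, because Visit 6 is complete. No other criterion mentions the drug. Section 3.1 allows continuation if the drug counts as established. Section 4.7.2 is breached on Day 1.

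6. Case during the study. Suppose seizure control worsens within the 48 weeks and a site starts phenytoin. Section 3.4 allows it; section 4.7.2 forbids it. This case does not depend on the rules of the previous study.

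7. Whether the information exists. Antiepileptics and concomitant medications are reviewed at Visit 1 and at every later Safety Period visit (7.1.1, 7.1.2, 7.2), and again at the follow-up call (7.4). Exposed patients can be identified without new data collection.

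**The case against.** The best defence is that this is a missing cross-reference. Section 4.7.1 sits in the part of the protocol that governs permitted and prohibited therapy, and it makes general permission subject to 4.7.2. Antiepileptics are medications, so a careful reader could apply 3.1 and 3.4 inside that limit. This softens the conflict but does not remove it: the synopsis, 3.1 and 3.4 do not send the reader to section 4.7, and 3.4 followed as written permits what 4.7.2 forbids.

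Three further points carry weight. First, every patient comes from INS011-17-103. If that study barred the same drugs, entry on a listed drug would be largely confined to starts in the interval of up to 2 weeks. Its rules are not in the documents, and they would not cover drugs started during the 48 weeks. Second, exclusion 7, together with the Visit 1 medication review, gives an attentive investigator a way to act, though not a common rule. Third, a breach would be handled as a protocol deviation: documented under 10.4, then classified and listed under 8.4.1.2. Section 3.3 also allows discontinuation where safety is at risk.

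Because of that third point, a reader might infer from the silence of 3.3 and 3.5 on prohibited therapies that the protocol contradicts itself on whether an exposed patient stays. It does not; those sections are silent, and deviation handling fills part of the gap.

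A reader might also take the clobazam figures in section 1.3 (about 2.5-fold higher cannabidiol exposure at 40 mg/kg/day) as the size of the problem and set them against the 40/20 = 2-fold dose range. The documents do not support this. Section 4.7.2 does not name clobazam, and section 1.3.2 reports an appreciable cannabidiol change with it only at the highest dose. The comparison would also set exposure against dose: the AUC geometric means in section 1.3 already differ by 2108/836 = 2.52-fold between 40 and 20 mg/kg/day.

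**Conclusion.** The point holds as a contradiction in the text. The synopsis, 3.1 and 3.4 permit antiepileptic changes without exception, 4.7.2 forbids at least two antiepileptics by name, and none of the 12 eligibility criteria refers to the listed therapies, although section 1.6 relies on those criteria as a safeguard. It should be corrected, since two safety rules in force give sites different instructions.

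Its size in patients is unknown: the number affected at entry could be anywhere from none upward, within the maximum of 30. The entry case assumes that a listed drug is in use at Visit 1 and that the investigator does not invoke exclusion 7. The on-study case assumes only that a site follows 3.4 as written.

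A reader might go further and infer that a given share of a dose group would be affected, or that families would turn to other cannabinoids between the two studies. The documents give no count of affected patients and describe no such use, and 3.1 intends enrolment to avoid an interruption of study drug. Nor do the documents show which of the conflicting rules is the intended one.

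**What to change.** - Reconcile the antiepileptic statements in the synopsis (Methodology), 3.1 and 3.4 with section 4.7.2, so that all four places give the same instruction.
- Align the eligibility criteria (synopsis and 3.2.2) and the removal section (3.3) with whichever rule is kept, including the position of a patient whose treatment changed between Visit 6 of INS011-17-103 and Visit 1.
- In the adverse event listings under 8.4.3.1, flag patients exposed to a therapy on the retained list, using the medication data already collected.

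Which drugs are restricted, and how exposed patients are managed, is for the sponsor to decide.

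The cost is protocol wording and one derived flag, with no new assessments. Because the change bears on patient risk, section 10.1 would require ethics approval of the amendment. The downside is that a few INS011-17-103 completers might be found ineligible, depending on the rule chosen.
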